5. REGISTRATION

- 5.1. To register a patient, the following documents should be completed by the research nurse or data manager and faxed ([contact]) or emailed to the UCCC CTO Study Coordinator:
 - 5.1.1. Signed patient consent form
 - 5.1.2. Eligibility Screening Worksheet and registration form
 - 5.1.3. HIPAA authorization form

6. TREATMENT PLAN

6.1. **Modified Atkins Diet (MAD) education and treatment plan:** The modified Atkins diet (MAD) approximates a diet with a 1:1 ratio of macronutrients: 1 part fat to 1 part protein and carbohydrate combined. It is referred to as “modified” because it is lower in carbohydrate content (< 20 net grams/day) than the original Atkins diet used for weight loss. In the MAD, fat and protein are not limited; however, protein intake may be assessed and limited if a patient is not able to achieve and/or maintain ketosis with < 20gm net carb intake as documented per daily food diary. Intake of protein in excess of that required for normal cell maintenance/repair can enter gluconeogenic pathways resulting in increases in serum glucose. A registered dietitian (RD), specially trained in managing ketogenic diets, will provide diet education and monitoring of diet-related side effects of the patients throughout the study period of 10 weeks, as per the schema. As part of this education, the RD will provide recommendations for meal planning and preparation, grocery shopping, completion of daily food diary and education related to management of potential adverse effects of the study diet.

6.1.1. Diet adherence: Diet adherence will be carefully monitored via daily patient/caregiver-generated food diary and ability to achieve and maintain ketosis. Weekly phone contact with RD will aid in ensuring compliance to the study diet by addressing any questions/concerns the patient and/or caregivers may have regarding any aspect of the study diet/processes. Body weight will be recorded each week for the first six weeks.

6.1.2. Diet-related adverse effects: Weight loss is common during the initiation period due to the diuretic effect of the diet. Electrolytes will be monitored weekly, oral hydration and adequate sodium intake encouraged, and caloric intake adjusted as needed. Constipation can be managed pharmaceutically with carbohydrate-free stool softeners and/or laxatives. Dietary modifications such as adequate oral liquid intake and increases in fiber-containing low carbohydrate vegetables may be necessary.

6.1.3. The patient will be educated on concomitant over-the-counter and prescription medications that could prevent the patient from attaining ketosis because of their carbohydrate content. See appendix VII

6.2. **Duration of Therapy:** In the absence of treatment delays due to adverse events, treatment may continue for 10-11 weeks or until one of the following criteria applies:

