STUDY NUMBER: **UCCI-BRAIN-16-01**

STUDY TITLE: Feasibility Study of Modified Atkins Ketogenic Diet in the Treatment of Newly Diagnosed Malignant Glioma

PRINCIPAL INVESTIGATOR: [name]
Adjunct-Associate Professor of Medicine
Division of Hematology/Oncology
[name]
[name]
[contact]
[contact]
[contact]

CO- INVESTIGATORS

[name], RD, CSO, LD
Clinical RD, Specialist in Oncology Nutrition
University of Cincinnati Cancer Institute
[name]
[name]
[name]
[contact]
[contact]
[contact]

STATISTICIAN:

[name]
Research Associate Professor of Psychiatry
Department of Psychiatry and Behavioral Neuroscience
University of Cincinnati Academic Health Center
[name]
[name]
[contact]
[contact]
[contact]

SUPPORT: UC Brain Tumor Center [name] Endowed Chair Fund

AGENT: Temozolomide

SCHEMA:

1. Diagnosis of High Grade Glioma (-28 days)
2. Pretreatment Visit 1: Meet with Physician and/or Nurse Practitioner (NP) for chemotherapy teaching. (day -28 to day -7)
 - a. Check lipid profile, complete metabolic panel, complete blood count with differential (CBC with diff), and hemoglobin A1C
 - b. Take medical history concerning pancreatitis, recent cholecystectomy or gallbladder dysfunction, diabetes, dairy allergies and/or lactose intolerance, in-born errors of metabolism
 - c. Obtain informed consent
 - d. Obtain tissue from biopsy or resection
3. Pretreatment Visit 2: Meet with Nurse Practitioner for chemotherapy teaching (day -28 to day -7)
 - a. Laboratory Correlatives
 - i. Serum beta-hydroxybutyrate (BHB)
 - ii. Complete metabolic panel, fasting serum glucose and insulin
 - iii. Vital signs, height, body weight, waist circumference
 - iv. Platelet mitochondrial labs
 - v. Neurocognitive testing (See Appendix VI)
 - vi. Quality of Life (FACT-Br) survey (See Appendix I)
 - vii. MRI planning scan
4. Pretreatment Visit 3: Meet with registered RD (RD) for nutritional education concerning carbohydrate restricted diet (Modified Atkins Diet (MAD)) (day -28 to day -7)
 - a. Diet education consultation with RD – 1.5 hours. Distribute week 1 food diary with education concerning completion (Appendix II)
 - b. Confirm above histories and labs
 - c. Random assignment to MAD ketogenic diet with radiation therapy day -7
5. Radiation/Chemotherapy commences (Day 0-Day 42)
 - a. Collect daily food diaries
 - b. Weekly visits with NP/MD
 - i. Serum BHB

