 - ii. Complete metabolic panel, fasting serum glucose and insulin levels
 - iii. Vital signs, body weight, waist circumference
 - iv. Quality of Life (FACT-Br) survey (See Appendix I)
 - c. Weekly telephone contact with RD to address diet related concerns
6. Radiation and temozolomide treatment terminated
 - a. Continued MAD until MRI (Day 43-70)
7. MRI and post-treatment visit #1 (approximately Day 70)
 - a. Meet with RD

- i. If patient wishes to discontinue research diet, RD will instruct patient on 3-day titration back to pre-study carbohydrate intake levels.
- ii. If patient wishes to continue longer term discuss supplement use to prevent nutritional deficiencies from long-term diet.
- b. Meet with attending physician
 - i. Review MRI findings
 - ii. Review post-intervention maintenance chemotherapy
 - iii. Laboratory Correlatives
 - i. Lipid profile, complete metabolic panel, complete blood count with differential (CBC with diff), and hemoglobin A1C
 - ii. Serum BHB
 - iii. Fasting serum glucose and insulin
 - iv. Vital signs, body weight, waist circumference
 - v. Platelet mitochondrial Labs
 - iv. Adverse Events
 - v. Performance Status
 - vi. Quality of life (FACT-Br) survey (See Appendix 1)
 - vii. Neurocognitive testing (See Appendix VI)
- 8. MRI and Ppost-treatment visit #2 (approximately day 126-154 after post-treatment MRI)
 - a. Meet with attending physician
 - i. Review MRI findings
 - ii. Review post-intervention maintenance chemotherapy
 - iii. Laboratory Correlatives
 - i. Lipid profile, complete metabolic panel, complete blood count with differential (CBC with diff) and hemoglobin A1C
 - ii. Serum beta-hydroxybutyrate
 - iii. Fasting serum glucose and insulin
 - iv. Vital signs, body weight, waist circumference
 - v. Platelet Mitochondrial Labs
 - iv. Performance Status
 - v. Quality of life (FACT-Br) survey (See Appendix 1)
 - vi. Neurocognitive testing (See Appendix VI)

[figure not shown]

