3. STUDY DESIGN

- 3.1. This is a single arm feasibility study.
- 3.2. Study Diet: Patients will be screened for study eligibility and written informed consent will be obtained prior to enrollment. Patients will meet with the registered dietitian (RD) one to four weeks prior to initiation of concurrent radiation and chemotherapy. At that visit, the RD will provide education on all aspects of MAD including meal planning and daily food diary completion (Appendix II). The diet will begin approximately 7 days prior to the initiation of concurrent radiation and chemotherapy and the patient will continue the study diet until the first post-radiation MRI, a time period of approximately 10 weeks. We will obtain blood to assess serum BHB, fasting insulin and glucose, and other chemistries as well as body weight weekly, according to the standard of care, while on chemotherapy and radiation therapy. Participants will receive weekly phone calls from the RD to address any questions or concerns the patient may have regarding the MAD and daily food diary. A food diary (Appendix II) will be used to assess adherence during the 10-week period. All macronutrient intake from food diaries will be entered by study agent into nutrient analysis software. This macronutrient breakdown will be utilized to identify potential problematic macronutrient intake which may be preventing patient from achieving ketosis. This is available online as well.
 - 3.2.1. Temozolomide and radiation will be given according to the standard protocol described by Stupp et al.ⁱ Patients will receive 75 mg/m² of temozolomide concurrent with radiation therapy at standard dose. The dose of radiation and/or chemotherapy and/or steroid may be modified by the attending physician based on clinical indications.
 - 3.2.2. Correlative platelet mitochondrial studies will be drawn on the pre-treatment visit #2, the post-treatment visit #1 and the post-treatment visit #2. Patients are already having blood drawn at these visits as standard of care. This sample will be transported within 6 hours to the laboratory **[name] at Cincinnati Children's Hospital Medical Center** for assessment of mitochondrial respiration in the platelets.
 - 3.2.3. QOL studies will be done at the pre-treatment visit #2, pre-treatment visit #3, weekly during chemotherapy and radiation, at the post-treatment visit #1 and then at post-treatment visit #2

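### The schedule stops weekly dietitian calls at Day 42, while the diet runs to about Day 70 and sections 3.2, 6.1 and 6.1.1 imply that contact continues

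*Combined protocol and SAP*

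**What the plan says.** Section 6.1 gives the RD responsibility for "diet education and monitoring of diet-related side effects of the patients throughout the study period of 10 weeks, as per the schema". The sentence sets a duration and refers to the schema for the detail.

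Section 3.2 says "Participants will receive weekly phone calls from the RD to address any questions or concerns the patient may have regarding the MAD", with no stopping day. The sentence after it says "A food diary (Appendix II) will be used to assess adherence during the 10-week period". Section 6.1.1 also relies on weekly RD phone contact to support compliance, again without an end date.

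The schema's text list is narrower. Item 5 is headed "Radiation/Chemotherapy commences (Day 0-Day 42"), and inside it stand 5a, "Collect daily food diaries", the weekly NP/MD visits (5b), and 5c, "Weekly telephone contact with RD to address diet related concerns". The only entry under item 6 is "Continued MAD until MRI (Day 43-70"). The next listed contact is item 7, post-treatment visit #1 at about Day 70, which includes a meeting with the RD and collection of adverse events.

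In Appendix IV, as extracted, the RD Consult row is marked at pre-treatment visit #3 and in the Day 0-42 block only, while the diet row is marked through post-treatment visit #1.

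**The concern.** Section 6.1 refers to a schedule that does not deliver what the section promises. A coordinator working from the schema or Appendix IV would stop the calls at Day 42. One working from 3.2 or 6.1.1 would continue them. Patients in the same study could be handled differently.

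If the calls stop, patients remain on a restrictive diet for four weeks with no planned contact in which staff could hear about problems. The RD review for low BHB (7.1) and the evaluation of raised fasting glucose (7.3) are triggered by blood tests that the schema next lists at about Day 70. Removal from the diet for Grade 3 or 4 diet toxicity (7.2) depends on someone learning of the event. Sections 6.2 and 6.3.1 show that the interval belongs to the treatment period: treatment lasts 10-11 weeks, which fits the diet and not the six weeks of chemoradiation, and toxicity is followed for 14 days after treatment stops (or until progression or death, if earlier).

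**Working it through.** **Inputs**
- Diet start: about Day -7 (3.2; schema item 4c).
- Diet end: first post-radiation MRI, about Day 70 (3.2; schema items 6 and 7).
- Last day of the block that holds the weekly RD calls: Day 42 (schema item 5).
- Next RD contact: meeting at about Day 70 (schema item 7a).
- Planned sample: 30 evaluable patients (3.3).

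**Step 1. Reproduce the plan's duration.** Diet length = 70 - (-7) = 77 days, and 77/7 = 11.0 weeks. Counted from Day 0 it is 70/7 = 10.0 weeks. Both match the 10-11 weeks in 6.2; section 3.2 rounds to about 10.

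**Step 2. Size of the gap.** 70 - 42 = 28 days, and Day 43 to Day 70 counted inclusively is also 28.

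| Counting rule | Share of diet days |
|---|---|
| 28 of 77 (Day -7 to Day 70) | 36.4% |
| 28 of 78 (inclusive count) | 35.9% |
| 27 of 77 (Day 70 visit counted as contact) | 35.1% |
| 28 of 70 (nominal 10 weeks) | 40.0% |

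**Step 3. Calls missing from the schedule.** A weekly rhythm after Day 42 gives Days 49, 56 and 63; the fourth slot, Day 70, is the RD meeting. If the first call is at Day 0, calls on Days 0 to 63 number 10, and 3/10 = 30% are missing. If the first is at Day 7, there are 9, and 3/9 = 33%. The interval between planned RD contacts rises from 7 days to 28.

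**Step 4. Did the authors mean the calls to stop?** Compare how the text limits other weekly items.
- 3.2: bloods "as well as body weight weekly, according to the standard of care, while on chemotherapy and radiation therapy". The next sentence, on RD calls, carries no such limit.
- 6.1.1: weight is weekly for the first six weeks; RD phone contact has no end.
- Schema item 5c: RD calls fall inside Day 0-42, alongside the visits and bloods.

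The body text limits a measure where it means to, so it favours calls throughout the diet. The text list points the other way.

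**Step 5. What else covers Day 43-70.**
- Daily food diary with nutrient analysis (3.2). Diary collection is listed in the schema only under Day 0-42, so these diaries may not be seen before about Day 70. The Appendix IV diary row is too damaged to settle this.
- Optional urine Ketostix and advice to report constipation (Appendix VIII).
- Recording of any event the patient reports (8.4), SAE reporting, and the weekly study team meeting.
- Adverse-event collection at about Day 70 (schema item 7).
- Weekly electrolytes, which 6.1.2 promises with no end date but the schema does not list after Day 42.

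Apart from the electrolyte sentence, read literally, none of these is a planned contact with the patient between Day 42 and Day 70.

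**The case against.** The strongest reply is that the calls are already planned. Sections 3.2 and 6.1.1 promise them without limit, and item 6 of a summary list merely omits a line. That reading is natural, and on it the change is only to the schedule text. It does not remove the conflict, because staff who follow the schedule would still stop.

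Second, the visible schema is not the whole schema: a figure follows the list and cannot be seen here, and Appendix IV is partly garbled. This stands. The point is established for the text list, with Appendix IV as support only.

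Third, a reader might infer that a primary or secondary objective is compromised. The documents do not support that. Objectives 1.2.3 (compliance) and 1.3.2 (safety) are worded as concurrent with radiation, the latter also with chemotherapy, and the ketosis criterion in 10.5.1 covers only the six weeks of chemoradiation.

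Fourth, a reader might infer that many diet side effects would be lost. Nausea, fatigue, food refusal and dehydration are listed in 8.2 as immediate short-term effects, and 6.1.2 places common weight loss at initiation. By Day 43 a patient has been on the diet about seven weeks (43 + 7 = 50 days). The documents give no figure for events missed, and events are still asked about at about Day 70.

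Fifth, the end of weekly weights and most bloods with chemoradiation might look like part of the same contradiction. It is not: the schema, 3.2 and 6.1.1 are consistent on it. Nor should the open-ended electrolyte sentence in 6.1.2 be cut back to match, since that would remove a stated safeguard from the very interval in question.

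**Conclusion.** The inconsistency is real and modest. Followed as scheduled, 28 of about 77 diet days (36%; 35-40% under other day counts) have no scheduled RD call or clinic visit. If 3.2 and 6.1.1 govern, the schedule omits about three planned calls per patient. Either way the schedule needs correcting.

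The consequence lies in patient safety and in adherence support over the 10-week diary period, not in the main analysis. The conclusion assumes a diet start at about Day -7, an MRI at about Day 70, and that the missing schema figure does not itself show later RD calls. It is worth changing because the cost is small.

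**What to change.** 1. In schema item 6, add weekly RD telephone contact at about Days 49, 56 and 63, with any diet side effects that the patient reports recorded under 8.4.
2. In Appendix IV, mark the RD Consult row for those weeks and for the Day 70 RD meeting in item 7a.

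Leave 6.1.2 as it is. No extra blood draw, home weight or new instrument is needed.

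The longest planned interval between RD contacts after Day 42 falls from 28 days to 7. The cost is at most 3 × 30 = 90 calls by the RD already assigned, fewer if patients stop the diet early. At an assumed 10-20 minutes per call (not in the documents), that is 90 × 10/60 = 15 hours to 90 × 20/60 = 30 hours over the whole study. If 3.2 and 6.1.1 already govern, the calls are in the plan and the only cost is the text amendment.

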6.2.1. Intercurrent illness that prevents further administration of treatment

6.2.2. Unacceptable adverse treatment related toxicity, NCI CTC AE version 4.0. Grade 3 or 4 that fails to recover to baseline or < Grade 3 in the absence of treatment within 4 weeks

6.2.3. General or specific changes in the patient’s condition that render the patient unable or unsuited for further participation in the judgment of the investigator,

6.2.4. Patient decision to withdraw from treatment (partial consent) or from the study (full consent),

6.2.5. Pregnancy during the course of the study for a childbearing participant.

6.2.6. Death.

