7. DOSING DELAYS / DOSE MODIFICATIONS

- 7.1. If serum ketosis is not obtained (BHB ≥ 0.5 mM), the RD will review the daily food diary (Appendix II) to determine if the calculation of net carbohydrate intake is accurate and to modify the diet to obtain ketosis.
- 7.2. If patient develops Grade 3 or Grade 4 toxicity determined to be related to the diet then patient will be removed off diet. Toxicity can be determined by research coordinator, primary investigator or co-investigator.
- 7.3. If patient has a fasting glucose level >90 mg/dl, it will precipitate an evaluation of dietary intake and/or medical issues (i.e. infection).
- 7.4. If patient is admitted to the hospital while on study/diet, compliance with the diet will be up to the admitting physician and the patient. If the admission is secondary to the diet/protocol, this will be documented as a serious adverse event and the diet will be discontinued to till patient returns to Grade 1 level and then the diet can be resumed. If the patient has a second serious adverse event from the protocol, then the patient will be permanently removed from the diet. Please see section 6.2

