10.4.1.3. Clear progression of non-measurable disease

10.4.1.4. Any new lesion

10.5 Statistics

10.5.1 Ketosis will be defined as serum BHB > 0.05 mM throughout 6-week period of radiation and chemotherapy. We hope to find that in our given sample of 30 patients at least 50% will meet this criteria. We will compute a 95% confidence interval for this rate to estimate the likely range in the target population. A 10% increase in glutamate within the tumor on the post-RT MRI as compared to the pre-RT MRI will be considered evidence that the tumor is using ketones as fuel by the conversion to glutamate.

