APPENDIX IV

	Pre-Treatment Visit #1	Pre-Treatment Visit #2	Pre-Treatment Visit #3	Temodar plus radiation therapy (RT)	Temodar and RT completed	Post-Treatment Visit #1	Post-Treatment Visit #2
	D-28 to day -7	-28 to day -7	D-28 to day -7	Day 0-42	Day42	Appx. Day 70	2-3 months after PTV1
				Weekly	Daily		
Informed Consent	X						
Medical History	X			X		X	X
Concomitant Medications / Treatments	X		X	X		X	X
Physical Exam	X			X		X	X
Vital Signs/Weight/ Waist Circumference	X	X		X		X	X
Lipid profile, CBC with diff, hemoglobin A1C,	X					X	
Serum BHB		X		X		X	X
Complete Metabolic Panel, fasting glucose, fasting insulin		X		X		X	X
Platelet Mitochondrial Labs		X				X	X
MRI		X				X	X
Food diary				X X		X	
	Pre-Treatment Visit #1	Pre-Treatment Visit #2	Pre-Treatment Visit #3	Temodar plus radiation	Temodar and RT completed	Post-Treatment Visit #1	Post-Treatment Visit #2

			ent Visit #3	therapy (RT)			
	D-28 to day -7	-28 to day -7	D-28 to day - 7	Day 0-42	Day42	Appx. Day 70	2-3 months after PTV1
Adverse Events				Weekly	Daily	X	X
Performance Status	X			X		X	X
Quality of Life (FACT-BR)		X		X		X	X
Neurocognitive Testing		X				X	X
RD Consult (initial in person and then via phone)			X	X			
Treatment							
MAD			X	X	X	X	
Temodar and RT (Stupp)				X	X		

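### Sections 6.2.2, 7.2 and 7.4 disagree on the action, the recovery condition and the cause when toxicity takes a patient off the diet

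*Combined protocol and SAP*

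**What the plan says.** Section 6.2 (Duration of Therapy) says that "treatment may continue for 10-11 weeks or until one of the following criteria applies". One criterion, 6.2.2, is "Unacceptable adverse treatment related toxicity, NCI CTC AE version 4.0. Grade 3 or 4 that fails to recover to baseline or < Grade 3" within 4 weeks off treatment.

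Section 7.2 says: "If patient develops Grade 3 or Grade 4 toxicity determined to be related to the diet then patient will be removed off diet". It gives no recovery level and no route back.

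Section 7.4 deals with hospital admission: "If the admission is secondary to the diet/protocol, this will be documented as a serious adverse event and the diet will be discontinued" until the patient is back at Grade 1, after which it may be resumed. It continues: "If the patient has a second serious adverse event from the protocol, then the patient will be permanently removed from the diet". It then refers the reader to 6.2.

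Treatment is not defined. Section 8.5.2.3 attributes adverse events to the study drug, and the title page names temozolomide as the agent. Section 8.5.2.4 is still an instruction to specify whether attribution is by component or for the regimen as a whole.

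Section 10.5.1 asks for ketosis "throughout 6-week period of radiation and chemotherapy" and hopes for at least 50% of 30 patients. It does not say how a patient taken off the diet is counted, and 3.3 does not define evaluable.

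**The concern.** A stopping rule for toxicity should lead two staff members with the same patient to the same action. Here the action depends on which clause is opened first. The cause that triggers it also changes: treatment related in 6.2.2, diet related in 7.2, diet or protocol and then protocol alone in 7.4.

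Patient safety comes first: the diet could be resumed, or withheld for good, after the same event. The reading of compliance (1.2.3) and of the safety of the diet (1.3.2) is also at stake, because both depend on who leaves the diet and why. The 10.5.1 rate is affected only in a limited way, set out below.

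**Working it through.** The plan gives no diet-removal rate, toxicity rate or derivation of the 30 patients, so there is no figure to reproduce. The main check sets the clauses side by side.

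**1. Action and recovery condition.** Take a first diet-related Grade 3 event, with treatment in 6.2.2 read as the diet and a baseline below Grade 3.

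| Course of the event | 7.2 | 7.4 | 6.2.2 |
|---|---|---|---|
| Not admitted, Grade 1 by week 2 | Off diet, no return stated | Resumption route not engaged | Not met |
| Admitted, Grade 1 by week 2 | Off diet, no return stated | Interrupted, may resume | Not met |
| Admitted, Grade 2 at week 4 | Off diet, no return stated | Still interrupted | Not met (below Grade 3) |
| Admitted, Grade 3 at week 4 | Off diet, no return stated | Still interrupted | Ended |

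Rows 1 and 2 have the same grade and recovery, yet only the admitted patient has a written route back. In row 2, 7.2 and 7.4 both apply and differ. In row 3 the patient has met the recovery level of 6.2.2 but not that of 7.4.

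**2. Can the clauses be fitted together?** Two readings are possible.

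- Reading A: removal under 7.2 is temporary. The row 2 patient may resume. For row 1 the text does not say whether the 6.2.2 level or the 7.4 level governs return.
- Reading B: removal under 7.2 is final, and resumption under 7.4 serves only admitted events below Grade 3. The row 2 patient never resumes, and the recovery period in 6.2.2 has no work to do for diet toxicity.

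The text permits both, with opposite results in row 2.

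**3. Cause.** The diet runs from about Day -7 (3.2) to about Day 70 (Schema): 77 days / 7 = 11 weeks, or 10 weeks counted from Day 0. Chemoradiation runs Day 0 to 42: 42 / 7 = 6 weeks. The 10-11 weeks in 6.2 therefore fit the diet, and the only plan in Section 6 is the diet. Against that, the Treatment block of Appendix IV lists temozolomide with radiation beside the diet, and 3.2.1 writes chemoradiation into the protocol. The diet reading of 6.2.2 is favoured but not stated. The word protocol in 7.4 remains open.

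**4. Reach into 10.5.1.** The window is the 6 weeks to Day 42. A stop between Day 43 and Day 70 (28 days) cannot change the result. Within the window, one patient is 1/30 = 3.3 points. To show only why the counting rule matters, assume 15/30 without removals (50.0%, exact 95% CI 31.3-68.7) and k assumed removals among patients who would have met the criterion. Exact limits are the beta quantiles B(0.025; x, n-x+1) and B(0.975; x+1, n-x).

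| k | Counted as failures | Dropped |
|---|---|---|
| 1 | 14/30 = 46.7% (28.3-65.7) | 14/29 = 48.3% (29.4-67.5) |
| 3 | 12/30 = 40.0% (22.7-59.4) | 12/27 = 44.4% (25.5-64.7) |
| 6 | 9/30 = 30.0% (14.7-49.4) | 9/24 = 37.5% (18.8-59.4) |

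If the three removed patients would have failed anyway, counting them as failures leaves 15/30 = 50.0%, and dropping them gives 15/27 = 55.6%. If removal is unrelated to ketosis and patients are replaced, the expected rate does not change. The direction therefore depends on a rule that the plan does not give.

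**The case against.** The best defence is that the clauses form a sequence. The recovery period in 6.2.2 runs with treatment already off, so it presupposes the removal that 7.2 orders. Section 7 is headed as delays and modifications, only 7.4 calls removal permanent, and 7.4 points back to 6.2. Much of this stands: 6.2.2 and 7.2 do not conflict on every event, and a workable order can be built. But that order is Reading A. The text does not state it, and it leaves the return level for a non-admitted patient open.

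It is also fair that 8.5.1.6 and 8.5.1.7 already require attribution and action taken for each event, and that serious events attributed to the diet go to the monitoring board. That makes the fix cheaper. It does not settle which component attribution refers to.

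A reader might infer that temozolomide or radiation toxicity takes patients off the diet and so biases the feasibility rate downward. The documents do not support that. No passage says chemoradiation toxicity ends the diet, and the stated duration favours the diet reading. Nor is every removal a failure on 10.5.1: removals after Day 42 fall outside it and the counting of earlier ones is unstated. An interruption inside the 6 weeks may also break the continuous criterion whichever rule follows. Finally, objective 1.2.1 is ketosis concurrent with radiation, so losing the diet under chemoradiation is part of the question. Other routes off the diet (6.2.1, 6.2.3 and the admission sentence in 7.4) exist in any case, and aligning the cause terms would not close them.

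**Conclusion.** The inconsistency is real and should be corrected before staff have to apply it. For a first diet-related Grade 3 or 4 event with admission, the text supports both resumption and no return. Without admission, no return rule is given. The recovery level is Grade 1 in one clause and baseline or below Grade 3 in another. Chemoradiation toxicity is neither clearly included nor excluded, with the diet-only reading of 6.2.2 the more likely.

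The consequence is for patient safety and for the interpretation of compliance and diet safety. For 10.5.1 it is conditional on time off the diet inside the 6-week window and on how those patients are counted. Its size cannot be given from the documents; the figures above rest on assumed numbers of removals. A biased feasibility rate is not shown. Which clinical rule is right is for the sponsor and is not judged here.

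**What to change.** - Reconcile 6.2.2, 7.2 and 7.4 so that the cause term, the action and the recovery condition agree, and define treatment. The sponsor chooses the rule.
- Complete 8.5.2.4 by stating whether attribution is by component (diet, temozolomide, radiation) or for the regimen as a whole.
- State in 10.5.1 that patients taken off the diet during the 6 weeks stay in the denominator.
- Record a coded reason for each diet interruption or stop (diet toxicity, temozolomide or radiation toxicity, other illness, patient choice), including stops under 6.2.1, 6.2.3 and during admissions. Report 10.5.1 failures by reason beside the overall rate.

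The cost is wording in a few clauses, one coded field on the case report form and one table. No patients or procedures are added.
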